9.7.2 Safety analysis

Safety analyses will be performed on the safety set.

Frequency of safety events will be reported using numbers of participants with AEs, frequencies, incidence with 95% CIs. AEs will be tabulated by system organ class and preferred term for overall and for subgroup based on demographics and baseline characteristics.

Categorical variables will be reported using numbers of participants with AEs, frequencies, incidence with 95% CIs. Incidence will be analyzed using Pearson's chi-square or Fisher's exact test to determine if there are statistically significant differences.

Continuous variables will be reported using number of participants. Incidence will be reported using odds ratios and 95% CIs by simple logistic regression.

As a result of simple logistic regression, statistically significant variables will be reported using odds ratios and 95% CIs by multiple logistic regression.

AEs will be coded with the current version of the Medical Dictionary for Regulatory Activities (MedDRA). Past / concomitant medications will be coded according to the current version of the Korea Index of Medical Specialties (KIMS) coding system.

Safety analyses will be based on all participants treated, i.e. all participants who received at least one dose of JARDIANCE[®]. However, if data for participants who have been treated with JARDIANCE® beyond the scope of approved label are collected, these will be listed separately.

9.7.3 **Efficacy analysis**

Efficacy analyses will be performed on the efficacy set.

Efficacy analyses will be performed by subgroup based on demographics and baseline characteristics.

The standard descriptive statistical parameters (number of participants, mean, standard deviation, median, minimum, maximum, etc.) will be summarized.

The changes of the efficacy outcomes from baseline will be compared in an exploratory sense via paired t-test.

ONIS New Data Collection Protocol

Page 23 of 54

Study number: 1245-0323 Document number: c42645766-03

Proprietary confidential information © 2024 Boehringer Ingelheim International GmbH or one or more of its affiliated companies

For investigator's overall efficacy assessment, the number and percentage of participants will be presented. If the result of overall assessment is 'improved', it will be classified as 'effective'. If the result of overall assessment is 'unchanged' or 'aggravated', it will be classified as 'ineffective'.

'Effective' and 'ineffective' will be reported using numbers of participants, percentages with 95% CIs.

Categorical variable will be reported using numbers of participants, numbers of participants assessed as 'effective', effective rates and 95% CIs. Efficacy will be analyzed by Pearson's chisquire test or Fisher's exact test to determine if there are statistically significant differences.

Continuous variable will be reported using numbers of participants. Odds ratio and 95% CIs by simple logistic regression will be summarized.

To estimate any factors that are thought to influence an effective rate, logistic regression analysis and/or poisson regression will be conducted, and for statistically significant covariates the meaning will be described.

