9.2.3.2 Visit 2 (Follow-up 1: 12 weeks from Visit 1)

After 12 weeks from Visit 1, the participant returns for follow-up. The following data will be collected:

- Visit date
- Physical examination information (weight, BMI, blood pressure)
- Concomitant medication use
- Any changes in the JARDIANCE administration status
- Efficacy assessment: UACR (The measurement taken on the date closest to the visit date is collected.)
- Any changes in the laboratory test results (HbA1c, eGFR, serum creatinine, etc.: if available) if there is any lab result which was clinically significant compared to data before JARDIANCE® treatment
- Safety assessment: any AEs noted
- Study completion status (if applicable)
- Investigator's overall efficacy assessment (if applicable)

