9.3 VARIABLES

9.3.1 Exposures

Exposure to JARDIANCE® will be estimated as time from the first intake date to the last intake date of the participant during the study period.

The treatment dose is based on the current authorized label in Korea. The recommended dose of JARDIANCE® is 10mg once daily and it can be taken with or without food.

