11.2 ADVERSE EVENT AND SERIOUS ADVERSE EVENT COLLECTION AND REPORTING

The investigator shall maintain and keep detailed records of all AEs in their patient files.

Collection of adverse events

The study is a non-interventional study in real-world situation and will be conducted within the conditions of the approved marketing authorization. For this reason, the following AE collection and reporting requirements have been defined.

All serious adverse events, non-serious adverse events and AESIs occurring from the signing date on data release consent form to the end of the study need to be collected, documented and reported to the sponsor using the AE page of eCRF.

The investigator carefully assesses whether an AE constitutes an ADR using the information below.

Causal relationship of adverse event

The definition of an adverse reaction implies at least a reasonable possibility of a causal relationship between a suspected medicinal product and an AE. An adverse reaction, in contrast to an AE, is characterized by the fact that a causal relationship between a medicinal product and an occurrence is suspected.

Medical judgment should be used to determine the relationship, considering all relevant factors, including pattern of reaction, temporal relationship, de-challenge or re-challenge, confounding factors such as concomitant medication, concomitant diseases and relevant history.

Arguments that may suggest a reasonable causal relationship could be:

- The event is consistent with the known pharmacology of the drug
- The event is known to be caused by or attributed to the drug class
- A plausible time to onset of the event relative to the time of drug exposure
- Evidence that the event is reproducible when the drug is re-introduced
- No medically sound alternative etiologies that could explain the event (e.g. preexisting or concomitant diseases, or co-medications).
- The event is typically **drug-related and infrequent in the general population** not exposed to drugs (e.g. Stevens-Johnson syndrome).
- An indication of dose-response (i.e. greater effect size if the dose is increased, smaller effect size if dose is diminished).

Arguments that may suggest that there is **no reasonable possibility of a causal relationship** could be:

ONIS New Data Collection Protocol

Study number: 1245-0323

Document number: c42645766-03

Page 32 of 54

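### Section 9.7.2 analyses AE incidence per participant without observation time and fills the multiple logistic model by a significance screen; add a person-time rate and fix the covariates beforehand

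*Protocol*

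**What the plan says.** Protocol 9.7.2 sets the safety measure: "Frequency of safety events will be reported using numbers of participants with AEs, frequencies, incidence with 95% CIs". The unit is the participant, and no person-time denominator is named. Differences between categories are tested by Pearson's chi-square or Fisher's exact test. For continuous variables, "Incidence will be reported using odds ratios and 95% CIs by simple logistic regression".

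The multivariable step reads: "As a result of simple logistic regression, statistically significant variables will be reported using odds ratios and 95% CIs by multiple logistic regression". I take this to mean that significance in the simple model decides entry to the multiple model.

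Five other sections bear on observation time:

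- 9.7.1 plans follow-up at 12 and 24 weeks for everyone, and 9.2.3.3 makes Visit 3 the last one.
- 9.7.1.3 admits to the safety set anyone who took the drug and was followed up at least once.
- 9.3.1 says exposure "will be estimated as time from the first intake date to the last intake date of the participant during the study period". 9.3.3 lists follow-up duration and total duration of administration among the covariates.
- 11.2 collects AEs "occurring from the signing date on data release consent form to the end of the study".
- 9.9.1 acknowledges informative censoring and plans to characterise participants lost to follow-up.

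For the yes/no effective rate, 9.7.3 says that "logistic regression analysis and/or poisson regression will be conducted". It gives no rule for choosing between the two models and no variance method.

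**The concern.** There are two substantive points and one minor one.

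**Observation time.** A participant last seen at week 12 without an AE counts the same as one seen to week 24 without an AE. If some leave early, the reported proportion is no longer a 24-week risk but a mixture of risks over different windows. If early leaving is also linked to a covariate such as age, that covariate can appear protective merely because its carriers were watched for less time. Incidence is the primary outcome (9.3.2.1), and section 7 says the surveillance results are reflected in the approved product information.

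**Significance screen.** Choosing variables by their univariable p-value tends to inflate the odds ratios that survive. It yields confidence intervals that ignore the selection, and it can discard a confounder whose effect shows only after adjustment.

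**Effective-rate model (minor).** Logistic regression gives an odds ratio and Poisson regression a ratio of proportions. Leaving both open leaves the effect measure open.

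**Working it through.** The protocol gives no expected AE rate, dropout, alpha, power or precision. The target of 250 rests on prevalence and market conditions (9.5), so there is no planned figure to reproduce. What follows illustrates size under stated assumptions.

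**1. Crude proportion against 24-week risk**

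Assumptions: constant hazard; true 24-week risk R of 10%, 30% or 50%; a share f observed only to week 12; the rest observed to week 24; leaving unrelated to AE risk.

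- h = -ln(1 - R)/24 per week, so the 12-week risk is R12 = 1 - exp(-12h) = 1 - sqrt(1 - R).
- Crude = (1 - f) x R + f x R12.
- Example, R = 30%: R12 = 1 - sqrt(0.70) = 0.1633. With f = 10%, crude = 0.9 x 0.30 + 0.1 x 0.1633 = 0.2863. With f = 40%, crude = 0.6 x 0.30 + 0.4 x 0.1633 = 0.2453.

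| R | f = 10% | f = 20% | f = 40% |
|---|---|---|---|
| 10% | 9.5% (-4.9%) | 9.0% (-9.7%) | 8.1% (-19.5%) |
| 30% | 28.6% (-4.6%) | 27.3% (-9.1%) | 24.5% (-18.2%) |
| 50% | 47.9% (-4.1%) | 45.9% (-8.3%) | 41.7% (-16.6%) |

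Relative errors are in brackets. With f = 0 the error is zero.

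**2. First events over person-time under the same assumptions**

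Expected time to first event or end of observation at T is (1 - exp(-hT))/h. Expected first events per participant are (1 - f) x R + f x R12, and expected person-time is that same quantity divided by h. The ratio is h whatever f is, so the rate is unaffected by the share leaving early.

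**3. Odds ratio between two groups with the same hazard (R = 30%)**

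- f = 20% in both groups: OR = 1.00.
- f = 10% against 30%: proportions 0.2863 and 0.2590, OR = (0.2590/0.7410)/(0.2863/0.7137) = 0.87.
- f = 10% against 40%: OR = (0.2453/0.7547)/(0.2863/0.7137) = 0.81.

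So the distortion appears only when early leaving differs by covariate.

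**4. Significance screen**

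For k independent null factors tested at 5% (k and the level are assumed), the chance of at least one false selection is 1 - 0.95^k: 23% for k = 5, 40% for 10, 54% for 15 and 64% for 20.

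**5. Poisson model for a binary outcome**

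Model-based Poisson variance takes p where the binomial has p(1 - p), so the standard error is too large by 1/sqrt(1 - p): 1.41 at p = 50%, 1.83 at 70%, 2.24 at 80%. A simulation of two equal groups (total 250, true rates 70% and 85%, 20,000 data sets) gave:

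| Model | 95% CI coverage (log ratio of proportions) | Rejection rate |
|---|---|---|
| Poisson, model-based variance | 100% | 9.7% |
| Poisson, robust variance | 95.2% | 81.6% |
| Logistic | not computed | 81.6% |

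The log ratio of proportions was almost unbiased (about 0.001). Only the model-based variance causes trouble, and it errs on the conservative side.

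**The case against.** The strongest reply is that follow-up is planned to a fixed 24 weeks, and over a fixed window logistic regression for whether a participant had an AE is a valid model. That stands. A reader might infer that both the safety and the efficacy analyses are mis-specified; the documents do not support this. The size of any bias depends on early leaving, which the protocol does not quantify. Poisson regression for a binary outcome is sound with robust variance, and 9.7.3 does not say that model-based variance will be used. The statistical analysis plan, not available here, may settle it.

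A reader might also take the completion-status item at Visit 2 as a planned exit, or assume that stopping the drug ends observation. Neither follows. The item can simply record an early exit. Section 11.2 collects AEs to the end of the study rather than to last intake, and 9.9.1 provides for contacting participants who are lost. A participant who stops the drug early may still be observed to week 24.

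The protocol also lists follow-up duration as a covariate. This helps less than it seems: 9.7.2 does not commit to adjusting for it. Because AEs can lead to discontinuation (an outcome in 9.3.2.1), duration can be partly a consequence of the event, and entering it as a predictor invites reverse causation.

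Finally, all analyses are declared exploratory (section 4). That lowers the stakes. It does not correct a proportion that mixes observation windows, nor an odds ratio reported after unacknowledged selection. Both methods are written into 9.7.2 and are not merely details left open.

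**Conclusion.** The point holds as an improvement to stated methods. The incidence measure and its comparisons in 9.7.2 ignore observation time, while the safety set admits participants with a single follow-up and the data needed for a rate are collected. If 10% to 40% of participants are seen only to week 12, the crude proportion falls about 4% to 19% (relative) below the 24-week risk. This rests on constant hazard and risks of 10% to 50%; if AEs cluster soon after the start, the shortfall is smaller. Odds ratios are affected only when early leaving varies with the covariate (0.81 in place of 1.00 for 40% against 10%, at a 30% risk).

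The significance screen is weak whatever the follow-up, with a 23% to 64% chance of at least one false selection across 5 to 20 independent null factors. The undecided model in 9.7.3 is minor. Nothing here shows that the planned models are invalid.

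**What to change.** 1. **Incidence.** Keep the crude proportion. Add first events per 100 patient-years with an exact 95% CI. Match numerator to person-time in one of two ways: onset from first intake to the end of AE observation, over that follow-up time; or on-treatment events, over exposure time. Do not combine AEs collected to study end (11.2) with exposure that stops at last intake (9.3.1), because off-drug events would then have no person-time. The rate does not remove informative leaving, so keep the description of lost participants in 9.9.1.
2. **Multiple model.** Replace the significance screen with one small covariate set fixed beforehand from baseline data already collected, for example age, sex and history of type 2 diabetes, with its size limited by the number of events.
3. **Effective rate (minor).** In 9.7.3 name one model and effect measure: logistic regression, or Poisson regression with robust variance.

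The cost is some extra programming and tables, with no new data collection. If baseline eGFR is added to the model, participants without a value drop out, since 9.2.3.1 collects it only where available.

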	Patients who have provided informed consent and signed the data release consent form			
	Exclusion criteria:			
	 Patients with previous exposure to JARDIANCE® 			
	 Patients with hypersensitivity to empagliflozin or to any of the excipients 			
	Patients with type 1 diabetes			
	Patients with history of diabetic ketoacidosis (DKA)			
	 Patients with rare hereditary conditions of galactose intolerance, 			
	the Lapp lactase deficiency or glucose-galactose malabsorption			
	 Patients who are pregnant or are breastfeeding or who plan to become pregnant during the study period 			
Variables:	Outcomes of safety:			
	All reported adverse events (AEs) in participants who take at least one dose of JARDIANCE®			
	Outcomes of efficacy:			
	Change in Urine Albumin-Creatinine Ratio (UACR) from baseline to 12 weeks and/or 24 weeks of treatment			
Data sources:	Participants' medical records			
Study size:	250 participants			
Data analysis:	All statistical analyses will be explorative in nature. Participant			
	characteristics will be reported using measures of central tendency (e.g., mean, median) and variance (standard deviation, quartiles) for continuous variables and using frequencies and percentages for count data. Frequency			

ONIS New Data Collection Protocol

Page 9 of 54

Study number: 1245-0323 Document number: c42645766-03

Proprietary confidential information © 2024 Boehringer Ingelheim International GmbH or one or more of its affiliated companies

	of safety events will be reported using frequencies and incidence with 95% confidence interval (CI). The changes of the efficacy outcomes from baseline will be compared in an exploratory sense via paired t-test.	
Milestones:	Start of data collection: March 2024	
	End of data collection: November 2025	
	Interim report 1: January 2024	
	Interim report 2: January 2025	
	Final study report: February 2026	

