9.7.1 Analysis sets

250 participants will be entered in this study, and each participant will be followed for baseline, short term (12 weeks) follow-up, and long term (24 weeks) follow-up. The safety analysis will comprise all participants who took JARDIANCE® with at least one time of safety follow-up.

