9.7.1.3 Number of participants for safety assessment

These include those who signed the data release consent form to participate in this study, took JARDIANCE® once at least, and were followed up by the investigator once or more. Reflecting the MFDS guideline, the cases below shall be excluded from safety analysis (defined below) set in the following order:

- a. Participants who did not signed (signature missing), or participants who signed on the data release consent form of JARDIANCE® CKD PMS prior to the contract date
- b. Participants who took JARDIANCE® prior to the contract date
- c. Participants who took JARDIANCE prior to signing the data release consent form
- d. Participants who have not taken JARDIANCE®
- e. Follow-up failure: Participants whose safety information cannot be obtained due to lost-to-follow-up
- f. Participants who were prescribed Jardiance for indications outside the local label

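### Section 9.7.2 assigns the primary safety incidences to two different populations: the safety set of 9.7.1.3, and everyone with at least one dose

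*Protocol*

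**What the plan says.** The protocol describes the population for the safety analysis in several places.

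- Section 9.7.2, first sentence: "Safety analyses will be performed on the safety set".
- Section 9.7.1.3 defines that set. Participants must have signed the data release consent form, and they "took JARDIANCE® once at least, and were followed up by the investigator once or more". It then adds, with reference to the regulator's guideline, that "the cases below shall be excluded from safety analysis (defined below) set in the following order", followed by items a to f.
- Section 9.7.2, last paragraph: "Safety analyses will be based on all participants treated, i.e. all participants who received at least one dose". The next sentence says only that data on treatment beyond the approved label will be listed separately.
- Section 9.7.1, introduction: "The safety analysis will comprise all participants who took JARDIANCE® with at least one time of safety follow-up". This requires a dose and a follow-up but mentions none of the other exclusions.

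Under section 9.3.2.1 every primary outcome is an incidence, and 9.7.2 reports incidences with 95% confidence intervals.

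**The concern.** The opening and the close of section 9.7.2 describe the same analyses but give them different denominators. Neither statement is called primary, sensitivity or supplementary, and no sentence says which prevails. An SAP that follows one of them departs from the other, so this is not a detail left for the SAP to settle.

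The stake is the denominator of every primary outcome, and for some participants the numerator too. The clearest effect comes from treated participants with no safety information. The one-dose sentence brings them into the denominator, where they can contribute no event and so act as event-free. For participants dosed before consent there is a further difficulty: section 11.2 starts AE collection at the date of consent, so the one-dose population would include people whose earliest exposure was not under AE collection.

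**Working it through.** The protocol has no figure to reproduce. The 250 in section 9.5 is an enrolment target without precision inputs. The check is therefore textual first, with an illustration of size after it.

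**Step 1. Each exclusion in 9.7.1.3 against the one-dose sentence in 9.7.2**

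| Exclusion | Safety set | At least one dose | Conflict? |
|---|---|---|---|
| a. Signature missing, or signed before the contract date | out | in, if treated | yes |
| b. Dosed before the contract date ("Participants who took JARDIANCE® prior to the contract date") | out | in | yes |
| c. Dosed before consent | out | in | yes |
| d. Never dosed | out | out | no |
| e. No safety information after loss to follow-up | out | in | yes |
| f. Prescribed for an indication outside the label | out | listed separately | largely matched |

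The conflict therefore lies in a, b, c and e. The introduction to 9.7.1 falls in between: its condition "with at least one time of safety follow-up" removes group e but leaves a, b and c in.

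On f, the two texts differ in scope. Item f concerns the indication only, while the sentence in 9.7.2 concerns any treatment beyond the approved label. A participant treated beyond the label in some respect other than indication stays in the safety set under 9.7.1.3 but is listed separately under 9.7.2. The two texts must be reconciled.

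**Step 2. Effect of group e on an incidence**

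Inputs: 250 treated (the target in 9.5, taken as all treated); fraction in group e assumed at 2%, 5%, 10% or 20%; AE incidence in the safety set assumed at about 20%. The protocol gives neither of the last two. With x participants having an AE and e participants in group e:

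- safety-set incidence = x / (250 − e)
- all-treated incidence = x / 250

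| e | Safety set | All treated |
|---|---|---|
| 5 | 49/245 = 20.0% | 49/250 = 19.6% |
| 12 | 48/238 = 20.2% | 48/250 = 19.2% |
| 25 | 45/225 = 20.0% | 45/250 = 18.0% |
| 50 | 40/200 = 20.0% | 40/250 = 16.0% |

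(The 5% row is 12.5 participants, taken as 12.) Exact 95% intervals overlap heavily. At e = 25 they are 15.0% to 25.8% and 13.4% to 23.3%. At e = 50 they are 14.7% to 26.2% and 11.7% to 21.1%.

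**Step 3. An event type that is never observed**

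The exact upper 95% limit with zero events is 1 − 0.025^(1/n). It is 1.49% for n = 245, 1.54% for 238, 1.63% for 225 and 1.83% for 200, against 1.46% for n = 250. Counting group e thus gives a tighter bound than the observed participants support.

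**Step 4. Groups a, b and c**

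Participants in these groups may have recorded events, so adding them can move the rate either way. If all those excluded had data and twice the assumed 20% rate, the all-treated figures would be (49 + 0.4 × 5)/250 = 20.4%, (48 + 0.4 × 12)/250 = 21.1%, (45 + 0.4 × 25)/250 = 22.0% and (40 + 0.4 × 50)/250 = 24.0%.

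**The case against.** The strongest reply is that the protocol largely shows which set it means. Section 9.7.1.3 is the only itemised definition, it is worded as mandatory, and it cites the regulator's guideline. Section 9.7.2 opens with it, 9.7.1 also requires follow-up, and 9.7.1.4 builds the efficacy set on the exclusions in 9.7.1.3. On that view the closing sentence is loose wording. This is a good reason to choose the 9.7.1.3 set as primary. It does not remove the conflict, because the closing sentence gives its own explicit definition and assigns the same analyses to it.

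The reply is also right that the affected groups may be small. Prior exposure is an exclusion criterion (9.2.2.3), consent must precede participation (10.1), and 9.9.1 plans to obtain AE information from participants lost to follow-up. The analyses are declared exploratory, and no decision threshold depends on a rate.

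Three stronger readings are tempting, and the documents do not support them.

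- A reader might infer that all six exclusions conflict with the one-dose sentence. Item d is implied by it, and f is largely covered by the separate listing.
- A reader might take the abstract as a further population, since it says "All reported adverse events (AEs) in participants who take at least one dose of". That line stands under the safety outcomes and says which events count. It does not define an analysis set.
- A reader might conclude that exclusion conceals adverse events. Section 11.2 requires all AEs from consent onward to be documented and reported to the sponsor whatever the analysis set. What an excluded participant loses is a place in the incidence tables.

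**Conclusion.** Wrong as written. Section 9.7.2 gives two populations for the primary safety incidences, and they differ for treated participants under exclusions a, b, c and e. Group e can only lower each incidence under the one-dose sentence. Groups a, b and c could move it in either direction.

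The size cannot be determined from the protocol. On the assumptions shown (about 2% to 20% of 250 in group e, AE incidence of 20% in the safety set), the all-treated figure runs from about 19.6% down to 16.0%. If few participants meet a, b, c or e, the numerical effect is small. The point does not rest on a large shift: the primary objective is safety, and its denominator should be fixed by one rule before the data are seen.

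**What to change.** 1. State in 9.7.2 that the set defined in 9.7.1.3 is the single primary safety population.
2. In the last paragraph of 9.7.2, delete the sentence beginning "Safety analyses will be based on all participants treated, i.e. all participants who received at least one dose". Alternatively, relabel it as a supplementary analysis limited to consented, treated participants with any post-dose safety information. The consent condition matters because section 9.4 confines source data to patients who consented to data release.
3. Keep the existing separate listing of treatment beyond the approved label. Reconcile its scope with item f, which covers indication only, and say whether listed participants are in or out of the incidence tables.
4. Report the number excluded under each of a to f, and list the collected AEs of consented, treated participants who are excluded.
5. Align the introduction of 9.7.1 by referring to 9.7.1.3 in place of its own shorter definition.

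The cost is protocol and SAP wording, and at most one extra table and one listing. No additional data collection is needed.
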